## **Method**

### ***Study design.***

This randomised controlled trial will use a 3 (time-point) x 3 (condition) mixed factorial experiment to investigate the effects of different delivery methods (digital human v audiotape v control) of relaxation on SBR after tape-stripping.

### ***Participants***

**Inclusion criteria.** Participants will be eligible for inclusion if they are over the age of 18 and can speak, read, and write in fluent English.

**Exclusion criteria.** Participants will be excluded from the study if they are allergic to adhesive tape, have any inflammatory skin diseases/immunological-related health problems,

are taking medication that affects immune functioning (e.g., prednisone), are pregnant, over the age of 60 or have hearing difficulties or vision loss.

**Sample size.** The sample size was calculated using G\*Power (Faul et al., 2007) with a *mixed factorial ANOVA*. A power level of .80 and a two-tailed significance level of  $\alpha = .05$  was chosen, with an expected effect size of  $f = 0.30$ , based on previous research investigating a relaxation intervention on SBR (Robinson et al., 2017). Using these parameters gives a required sample size of 75. Like previous tape-stripping studies, this will be increased by 20% to account for possible errors in the TEWL measurements (Law et al., 2020), giving a final sample size of 90 participants (30 participants per group).

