### *Primary outcome measures*

**Tape stripping and SBR.** The final SBR value for each site is determined by the TEWL readings from the three time-points. An overall TEWL reading comes from averaging 20 consecutive measurements with a standard deviation below 0.5 for each site and time point. To get the SBR percentage from the TEWL readings the following formula is used:  $(TEWL_{elevated} - TEWL_{recovery}) / (TEWL_{elevated} - TEWL_{baseline}) \times 100$  (Robles, 2007; Robles et al., 2009). A higher percentage means a higher SBR during the intervention period (faster wound healing). SBR values will be excluded if there is incomplete data, are more than two standard deviations above the mean, or sites are not within 30g/m^2h of each other (Law et al., 2020a). This outcome has concurrent validity with gravimetrically assessed absolute water loss rates (Fluhr et al., 2006).

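### The 80% power at N = 75 matches a three-measurement repeated-measures calculation, but SBR has no time-point dimension; actual unadjusted power is about 62% at 75 evaluable and 71% at 90

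*Protocol*

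**What the plan says.** All references are to the Protocol.

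- **Participants, Sample size.** The calculation was done in G*Power for a mixed factorial ANOVA. The targets open with "A power level of .80 and a two-tailed significance level of" .05. The effect size is f = 0.30, "based on previous research investigating a relaxation intervention on SBR". The result: "Using these parameters gives a required sample size of 75". Then "this will be increased by 20% to account for possible errors in the TEWL measurements", "giving a final sample size of 90 participants (30 participants per group"). Neither the G*Power test option nor the correlation among repeated measurements is given.
- **Study design.** The trial is a "3 (time-point) x 3 (condition) mixed factorial experiment".
- **Primary outcome measures.** "The final SBR value for each site is determined by the TEWL readings from the three time-points". The formula is (elevated − recovery) / (elevated − baseline) × 100, so baseline, post-stripping and post-intervention TEWL yield one percentage.
- **Procedure.** Three sites are stripped per participant. Baseline and post-stripping TEWL are both taken before the allocation envelope is opened; only the last reading follows the intervention.
- **Analysis.** SBR is to be analysed by a mixed factorial ANOVA and, in addition, an ANCOVA with covariates such as age, number of tape strips and degree of barrier impairment.

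**The concern.** A between-factors repeated-measures calculation assumes that the outcome is observed several times per participant and that the group comparison uses the average of those observations. Averaging reduces the error variance, so fewer participants are needed. Here the repeated factor in the design is time-point, but the primary outcome has already used up the three time-points in its own formula. There is one SBR per site and no series of SBR values over time. The effect size is also said to come from work on SBR, so it is already on the scale of the recovery score.

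Turning to raw TEWL does not restore the credit. Two of its three readings precede disclosure of the allocation and cannot carry an effect of condition.

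What is at stake is the power claimed for the primary hypothesis. If the credit is not earned, the chance of missing an effect of the assumed size is about 38% at 75, against the 20% that the paragraph implies.

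**Working it through.** **Inputs from the Protocol:** 3 groups, equal allocation; 3 time-points; f = 0.30; alpha 0.05; target power 0.80; N = 75, raised to 90 (75 × 1.2 = 90).

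**Assumed, not in the Protocol:** correlation ρ between repeated measurements, and the G*Power option used.

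All powers are tail areas of the noncentral F distribution with 2 and N − 3 degrees of freedom, beyond the 5% critical value.

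**1. Reproducing 75.** Repeated measures, between factors, with m measurements:

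λ = f² × N × m / (1 + (m − 1)ρ)

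With m = 3 and ρ = 0.5: λ = 0.09 × 75 × 3 / 2 = 10.125; critical F(2, 72) = 3.124; power = 0.803. Seventy-five is the smallest multiple of 3 that reaches 0.80.

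Other settings at f = 0.30:

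- m = 3, within-factor test, ρ = 0.5: N = 21.
- m = 3, within-between interaction, ρ = 0.5: N = 27.
- m = 3, between factors, ρ = 0, 0.3, 0.5, 0.7, 0.8: N = 39, 63, 75, 90, 96.
- m = 2, between factors, ρ = 0.3: also N = 75, but the design states three time-points.

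Among the settings tried for the stated 3 × 3 design, only the between-factors test with ρ = 0.5 gives 75.

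**2. Size of the credit.** With m = 3 and ρ = 0.5 the factor m / (1 + (m − 1)ρ) is 3 / 2 = 1.5. The calculation therefore treats 75 participants as if they carried 1.5 times the information of single values.

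**3. One SBR value per participant** (sites averaged). The factor becomes 1, so λ = f² × N:

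| Evaluable N | λ = 0.09 × N | Power |
|---|---|---|
| 75 | 6.75 | 0.619 |
| 90 | 8.10 | 0.707 |
| 108 | 9.72 | 0.792 |
| 111 | 9.99 | 0.803 |

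With equal groups, 80% needs 111 evaluable (37 per group). The f detectable with 80% power is about 0.37 at 75 and 0.33 at 90. This step uses only the Protocol's f, alpha and N; it does not depend on the inferred ρ.

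**4. Sites as the repeated factor instead.** If the three test sites were the repeated measurements and f = 0.30 were on the single-site scale, the step 1 formula applies with ρ as the between-site correlation:

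| Site correlation | Power at 75 | Power at 90 |
|---|---|---|
| 0.5 | 0.80 | 0.88 |
| 0.7 | 0.72 | 0.81 |
| 0.9 | 0.65 | 0.74 |

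**5. Covariate adjustment.** If three covariates explain a share R² of SBR variance, λ = f² × N / (1 − R²), with three fewer error degrees of freedom:

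- R² = 0.20: λ = 8.44, power 0.72 at 75; λ = 10.12, power 0.81 at 90.
- R² = 0.33: λ = 10.07, power 0.80 at 75.

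**The case against.** **The G*Power settings are inferred.** This is true. The exact match makes the between-factors option with ρ = 0.5 the likely source of 75, but the Protocol does not document it. A reader might treat the settings as established; they are not. The 62% and 71% do not depend on them.

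**SBR is defined per site, and there are three test sites.** This stands as a caveat. The Protocol does not say whether sites are averaged, and with sites as the repeated factor the power could be as high as 80% at 75. That needs a site correlation as low as 0.5 and an f on the single-site scale, neither of which the Protocol states. Its design section names time-point, not site, as the repeated factor.

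**The ANCOVA will recover power.** It may, and the 62% and 71% are unadjusted. The sample-size paragraph makes no assumption about variance explained, so the stated 80% cannot rest on it.

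**Further inferences that the Protocol does not support:**

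- That the 20% allowance is miscalculated because 90 to 75 is a loss of 16.7%. The Protocol says only that the number is increased by 20%, and 75 × 1.2 = 90 is correct. It never states a 20% loss.
- That pooling both relaxation arms against control restores 80% power and settles the matter. Hypothesis 1 expects both arms to beat control, and a pooled contrast can succeed when only one does. With two equally effective arms, f = 0.30 means a difference of 0.64 SD (0.30 × 3 / √2); each arm against control then has power of about 0.68 at 30 per group and 0.60 at 25.
- That a null result will be over-read. Nothing in the Protocol plans such an interpretation of Hypothesis 1.

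**Conclusion.** The sample-size statement is wrong as written: the 80% at 75 is not the power of the between-condition test on SBR as the Protocol defines it. The actual unadjusted power is about 62% at 75 evaluable and 71% at 90. The higher figure assumes that no SBR values are lost, although the extra 15 participants are there to cover TEWL measurement errors.

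This rests on f = 0.30 applying to the SBR score that is analysed, one value per participant with sites averaged, and no credit for covariates. That SBR has no time-point dimension is plain from its formula and needs no assumption. The route by which 75 arose is a strong inference only.

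A reader might conclude that the trial has to grow to 111. The documents do not compel that: 111 is what 80% would need under these assumptions, and a trial of 90 can proceed with its power stated correctly.

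**What to change.** Rewrite the sample-size paragraph in the Protocol so that it:

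- sizes the three-group comparison on a single SBR value per participant and says how the three test sites are combined;
- states power at f = 0.30 and alpha 0.05 as about 62% with 75 evaluable and 71% with 90, labelled unadjusted, with detectable f at 80% power of about 0.37 and 0.33;
- claims any gain from the ANCOVA only together with the assumed share of SBR variance explained (for example, about 20% gives about 81% at 90).

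If the sites are in fact meant to be the repeated factor, say so in the design and analysis sections, and give the site correlation and the scale of f.

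Cost: Protocol wording only. No added participants are required. The stated power becomes less favourable.

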### ***Procedure***

Ninety participants will be recruited from the local community using flyers, email lists and online advertisements between March and September (or until the sample size has been fulfilled). To ensure appropriate recruitment of Māori, researchers will use their connections with a Māori health organisation and the local community to talk, distribute flyers/information, network and build relationships (*whakawhanaungatanga*) with potential participants and their *whānau*. Participants interested in the study will be asked to email the researcher to fill in an eligibility screen and read the participant information sheet (PIS). Participants are offered the option of talking with *whānau* or support people if they would like to, before choosing to participate in the study. Eligible and interested participants will be then contacted to organise an appointment time when they are available.

Following salivary procedures and to reduce interference in the TEWL measures, participants will be asked not to drink caffeine, juice or alcohol 18 hours before the study and not eat, shower, exercise or apply moisturiser in the hour before the study (Law et al., 2020a). Appointments will be conducted in the afternoon as cortisol is typically higher in the morning (Fries et al., 2009), and in a ventilated room also in accordance with Tewameter probe recommendations (Robinson et al., 2015). When participants come into the clinic, they will be asked whether they would like to open with a karakia if appropriate to them. They will get the chance to re-read the PIS and ask any questions before deciding whether to give their free and full informed consent. After consent, the baseline questionnaires (demographics, health-related behaviours, and psychological variables) will be completed. Following this, baseline measures of cortisol and alpha-amylase (through a saliva sample) will be taken. Participants will be instructed to start wearing the wrist sensor for the rest of the experimental session (as a measure of heart rate and skin conductance).

After collecting baseline measures, the researcher will conduct the tape stripping procedure. Tape-stripping is a non-invasive experimental wound technique and standardised wound healing model that removes the outer layer of skin (the stratum corneum) through repeated application of the adhesive tape (Altemus et al., 2001; Irwin & Vedhara, 2007). By doing this, the skin cannot regulate water movement in and out of the skin, creating skin barrier disruption (Walburn et al., 2009). To get a baseline measure of this skin barrier function, a TEWL measurement will be obtained using a Tewameter 300 probe which measures the evaporation rate (g/m^2h) in the air layer next to the skin (Law et al., 2020b). TEWL, the skin's ability to prevent water loss, increases when the stratum corneum is disrupted and decreases when it heals. The probe must first be calibrated and preheated to 34°C (skin temperature), with constant ambient room conditions (Koschwanez & Broadbent, 2011). On each participant's non-dominant forearm, four 1cm^2 sites will be marked, with one

being the (undamaged) control. The probe will take one measurement every second for 60 seconds to measure the baseline values for each of the four sites one at a time. New pieces of tape will then be applied with pressure to the three test sites and gently peeled until the TEWL reaches 15 g/m^2h above baseline or 40 pieces of tape have been used. A TEWL measurement for each site will then be measured to examine the level of skin barrier impairment because of the tape-stripping. Immediately after the tape-stripping, participants will complete the post-tape-stripping questionnaire, the second saliva and TEWL measurements.

After the tape-stripping procedure, participants will be randomised to either the digital, audiotape, or control condition using a random online number generator by a researcher not involved in the study, completed in advance. Group allocation will be revealed after the researcher opens the sealed, opaque envelope containing each participant's assigned condition, after which the researcher will no longer be blinded to the conditions. As previous research has found that a relaxation session before and after tape-stripping can improve wound healing, this study will deliver the relaxation after the tape-stripping procedure for clinical practicality as there is often little time for relaxation to be done before an acute wound or pre-surgery (Robinson et al., 2015).

Participants allocated to the digital intervention will complete the digital human delivered relaxation intervention for 25 mins. During this time, the digital human will guide participants through progressive muscle relaxation and guided deep breathing. Those in the audiotape condition will be instructed to follow instructions on the computer (using the same script as the digital human condition). Those allocated to the control condition will be told to wait 25 minutes for their skin to recover while given magazines to read. The researcher will leave the room but will be next door in case there are any issues.

The researcher will return to the room once the intervention period is over, and participants will be asked to complete the post tape stripping questionnaires and the final TEWL measurements and saliva sample. The TEWL measured after the intervention period will be used to calculate SBR, an index of how fast the skin barrier recovered from the skin barrier disruption caused by the tape-stripping procedure. At the end of the session, participants will be given a \$30 voucher as compensation for their time.

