As stress can impair the wound healing process, several studies have investigated whether psychological interventions can reduce stress and improve wound healing. Psychological interventions can reduce physiological arousal, stress, and anxiety and alter patients' health behaviours and expectations of recovery and pain (Robinson et al., 2017). Systematic reviews by Robinson and colleagues (2017) and Geers and colleagues (2018) support the hypothesis that wound healing can be positively affected by a range of different psychological interventions including relaxation (Broadbent et al., 2012; Gouin, 2008; Han, 2002; Holden-Lund et al., 1988; Rice et al., 2001; Robinson et al., 2015), expressive writing (Koschwanez et al., 2013; Weunman et al., 2008), social support (Ginandes, 2003; Robles 2007) and yoga (Oswak et al., 2011; Rao et al., 2008).

Of these interventions, relaxation was found the most beneficial for wound healing outcomes (Robinson et al., 2017). Relaxation interventions can include deep breathing, guided imagery, biofeedback, and progressive muscle relaxation techniques. These techniques aim to counterbalance the stress response by reducing autonomic arousal and lowering stress hormones at the wound site, resulting in improved healing (Jacobs, 2001; Robinson et al., 2015). Relaxation interventions have been found to significantly increase the amount of collagen deposition (Broadbent et al., 2012), lower erythema (Holden-Lund et al., 1988), increase peripheral perfusion in foot ulcers (Rice et al., 2001), induce faster healing of stomach ulcers, and increase skin barrier recovery rates (Robinson et al., 2015). These findings demonstrate that relaxation is associated with better wound healing in a variety of different wound types.

Traditional methods of audiotapes and human-led relaxation are the most studied delivery method. Audiotapes are instructional and can be used from home, but they only provide passive information and guidance. Unlike audiotapes, human involvement can add

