### ***Intervention***

**Relaxation intervention delivered by the digital human.** Participants will interact with the digital human for 25 minutes. During this time, the digital human will guide participants through progressive muscle relaxation and guided deep breathing.

**Relaxation intervention delivered by the audiotapes.** Participants will be asked to listen to the audio recording on the computer to guide them through a relaxation intervention (the same progressive muscle relaxation and guided breathing script as the digital human) for 25 minutes.

**Control.** The control condition will not be provided with a relaxation intervention, only magazines while participants are told to wait and see how their skin recovers. Magazines have been used as a control condition in previous studies as a neutral activity to prevent participants from becoming too bored (Robinson et al., 2017).

In all conditions, the lights in the room will be dimmed to make the room more relaxing.

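### As written, control participants alone are told that their skin is recovering, an avoidable difference in instruction that could weaken the attribution of control contrasts to relaxation

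*Protocol*

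**What the plan says.** The control instruction appears twice in the protocol.

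- Procedure: control participants "will be told to wait 25 minutes for their skin to recover while given magazines to read".
- Intervention, Control paragraph: they receive "only magazines while participants are told to wait and see how their skin recovers".

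The two relaxation arms are described by the content of their session.

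- Digital human (Procedure): "the digital human will guide participants through progressive muscle relaxation and guided deep breathing".
- Audiotape (Procedure): "Those in the audiotape condition will be instructed to follow instructions on the computer (using the same script as the digital human condition").

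The Intervention section presents the magazines "as a neutral activity to prevent participants from becoming too bored", and hypothesis 1 identifies the control group by its magazines alone. The one feature that the Intervention section states as common to every arm is the lighting: "In all conditions, the lights in the room will be dimmed to make the room more relaxing". In the Introduction, the routes by which psychological interventions may act include changes to patients' "health behaviours and expectations of recovery and pain".

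**The concern.** The comparison with control is meant to show what relaxation does. Hypothesis 1 sets both relaxation arms against control on skin barrier recovery (SBR). Part of hypothesis 4 sets the digital human against control on anxiety, stress, pain and relaxation. If control participants are also told something about the recovery of their skin, and the others are not, these contrasts vary two things at once.

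The timing makes this relevant. The instruction comes at the start of the 25-minute period. That period lies between the post-stripping TEWL reading and the final one, which together with baseline define SBR, and the last self-ratings follow directly after it. The protocol itself treats expectations of recovery and pain as open to psychological influence. What is at stake is the interpretation of a control difference, not the validity of the randomisation.

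**Working it through.** No arithmetic applies. The point rests on no figure in the plan, and the sample size does not depend on it. The check is a comparison of the arm descriptions.

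**1. What each arm is told about the 25 minutes, as written**

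| Arm | Activity | Statement about skin recovery |
|---|---|---|
| Digital human | Relaxation led by the digital human | None described |
| Audiotape | Same relaxation script, played on a computer | None described |
| Control | Magazines | Described in both Procedure and Intervention |

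The two control sentences differ in wording but agree in substance: the period is linked to the skin recovering.

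**2. Is the statement described as common to all arms?** No. Dimmed lighting is the only feature so described.

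**3. Does the protocol give a reason to think the statement might matter?** Yes, as plausibility only. The Introduction says that interventions can alter expectations of recovery and pain. It does not say that a short explanation of a wait does so.

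**4. Which contrasts are touched?**

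- Hypothesis 1, each relaxation arm against control: touched.
- Hypothesis 4, digital human against control: touched.
- Hypothesis 2, and hypothesis 4 for digital human against audiotape: not touched. These arms share a script and neither is described as hearing the statement.

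**5. Could the planned analysis separate the two differences?** No. The Analysis section plans mixed factorial ANOVAs, and an ANCOVA with covariates such as age, number of tape strips and level of impairment. If the statement is given to every control participant and to nobody else, it coincides with the control arm, and no covariate can distinguish it from the absence of relaxation.

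**6. Direction and size.** A statement that raised expected recovery could improve control outcomes and narrow the contrast. One that drew attention to the wound could worsen control ratings and widen it. The documents support neither direction over the other and give no size for an instruction effect, so none is calculated here.

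**The case against.** The strongest reply is that the difference is inferred from silence. The two sections are short narrative summaries, and the differing control sentences read like paraphrase rather than a script. The relaxation script and the information sheet are not shown, and nothing says that the relaxation arms are *not* told that their skin will be recovering. This stands: the finding holds only for the protocol as written. If all arms do hear the statement, the two sections should say so, and the remedy is still an edit to the same sentences.

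A second reply is that everyone already knows about the wound. All participants consent, have three forearm sites stripped, rate their pain at three time-points and have TEWL measured repeatedly. This also stands, and it makes a large effect of one further sentence less likely. It does not remove the difference, because that awareness is common to the arms while the added sentence, as written, is not.

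A third reply is that control participants need some reason to sit for 25 minutes, and that exact wording often sits in an operating document. That is fair, but a neutral reason serves equally well. Nor would identical wording equalise expectations completely, since participants can see whether they have been given relaxation or magazines. The gain is modest.

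A reader might infer more: that the control comparisons are confounded, or that the self-reported stress mediator in hypothesis 3 is distorted. The documents support neither. They show a difference in described instruction and a plausible route, but no evidence that the instruction changes SBR, pain, stress or anxiety. Nor can the possible bias be expressed as a share of the planned effect, because that would require an instruction effect for which the documents offer no basis.

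**Conclusion.** The point holds in a limited form. As the protocol is written, control participants receive a statement about skin recovery that is not described for the other arms. This could weaken the attribution to relaxation of differences from control in hypothesis 1 and in the control part of hypothesis 4. Its direction and size are unknown.

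The conclusion rests on two assumptions: that the arm descriptions reflect what participants are actually told, and that a remark about recovery may influence expectations or attention. The randomised comparison of the three packages as delivered remains valid, and the contrasts between digital human and audiotape are unaffected. This is a minor, worthwhile improvement rather than a flaw that undermines the trial. It is best made before data collection, because the planned analysis could not separate the instruction from the arm afterwards.

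**What to change.** Give all three arms one identical neutral sentence before the activity starts, for example that the next step is a 25-minute period followed by the final measurements. Remove the recovery wording from the control instruction. Amend the Procedure and Intervention sections so that both carry this sentence and state that it is the same in every arm. The scripted difference between control and the other arms is then magazines against relaxation.

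The cost is one sentence in the researcher's instructions and matching edits in two sections. No time, staff or data are added, and the sample size and significance level do not change.
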